Photo-plethysmography (PPG) is a promising technology used in smartphones and smartwatches for heartrate and rhythm assessment. (6) To retrieve PPG measurements a photo-emitter of infrared light is coupled to a photo-receiver. The amount of infrared light absorbed or reflected by blood represents the systolic and diastolic phase. This technology has low costs and does not require additional hardware. Although easy to use and widely available, PPG measurements require good signal quality which may be affected by poorly perfused tissue or tremors. Especially in AF detection proper signal-noise assessment is important because of the irregular depolarization of the ventricles. To overcome these previous issues, we developed an automated PPG based diagnostic algorithm for the smartphone to detect AF. The test characteristics of this technique are robust and described elsewhere. (7)

Principal investigators and steering committee:

Dr. [name], cardiologist, Rijnstate hospital Arnhem

Dr. [name], geriatrician, North West Clinics, Alkmaar

Dr. [name], cardiologist Rijnstate hospital, Arnhem

Dr. [name], cardiologist, OLVG, Amsterdam

Dr [name], cardiologist, North West Clinics, Alkmaar

Participating centers:

Dijklander Hospital, Hoorn. Drs. [name], geriatrician.

Meander Medical Centre, Amersfoort. Drs. [name], geriatrician.

North West Clinics, Alkmaar. [name][name], geriatrician.

Rijnstate Hospital, Arnhem. [name], geriatrician.

Onze Lieve Vrouwe Gasthuis, Amsterdam. [name], cardiologist.

Aims of the project:

- a. To determine the rate of newly detected AF with repeated screening using a PPG based smartphone AF detection algorithm during follow-up visits at a geriatric outpatient center.
- b. To determine the rate of (paroxysmal) AF during follow-up visits.
- c. To evaluate the predictive value of a single measurement of NTproBNP at the baseline evaluation for the development of new AF.
- d. To evaluate the predictive value of the ABC Bleeding Risk Score, compared to the ATRIA Bleeding Risk Score, ORBIT Bleeding Risk Score, and HASBLED score.
- e. To evaluate adverse events such as major bleeding, stroke, death and cognitive disorders (Mild Cognitive Impairment or dementia), on the long term, namely: 3 years.

Hypothesis:

- a. We expect to find a rate of known AF of approximately 20%, and to find newly detected AF in 4 to 5% of the screened population.

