- b. We expect to find a rate of paroxysmal AF of 45 to 60%.
- c. We expect that the baseline level of NTproBNP or BNP will be predictive of the development of new AF, especially when combined with the findings of the comprehensive geriatric assessment (CGA) and CHA₂DS₂Vasc score.
- d. We expect a rate of major bleeding of 3-5% per year.
- e. We expect that the ABC bleeding score, using age, GDF-15 and high sensitive Troponin T, will be predictive of major bleeding in the geriatric population.

Design:

- a. Prospective multicentre cohort study
- b. We aim to include 1250 geriatric ambulatory patients
- c. Inclusion period will last for 6 months, with a consecutive follow up period of 6 months, at 3 years patient files will be accessed for adverse events
- d. Scheduled commencement of the study is October 2020
- e. Blinding: none
- f. Randomization: none

Ethical board:

- a. The Commission Human Bound Research region Arnhem-Nijmegen, The Netherlands, has exempted the protocol as a 'niet WMO-plichtig onderzoek'.
- b. The record number of this decision is: 2019-5889.

Methods:

- a. The PPG measurements will be performed with a specially designed app, this research app will be developed by Happitech. Every participating center will receive a smartphone in order to install the application.

- b. All newly referred patients of 65 years and older that visit geriatric outpatient services are eligible (including Fall clinic, Memory clinic, Pre-operative geriatric assessment clinic, or any other geriatric outpatient clinics that are led by a geriatrician).
- c. Patients will be sent printed informative material about the project together with their appointment details. This material includes the informed consent form. They are asked to read the material, and fill out the informed consent form at home. At arrival to the outpatient clinic remaining questions will be answered, and the informed consent form collected, scanned, and added to their electronic medical file.
- d. Inclusion criteria:
 - a. The patient is able and willing to give written informed consent or allows a representative to do so in their name.
 - b. The paper copy will remain at the outpatient clinic to serve as a backup.
- e. Exclusion criteria:
 - a. The patient has a pacemaker or implantable cardioverter defibrillator.
 - b. The patient is known with a severe dementia, MoCA \leq 15 points.

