- m. Patients will be classified as 'newly detected AF' if AF is detected by the PPG device and consecutively confirmed on a 12 lead ECG. These ECGs will be periodically collected by the research nurse, in order to be reviewed to confirm the diagnosis for research purposes, by an independent cardiologist ([name] or [name]).
- n. All positive measurements with the PPG based smartphone AF detection algorithm, will be assessed by an independent cardiologist ([name] or [name]).
- o. Patients known with AF will also be screened with the device in the same fashion, making it possible to estimate the proportion of paroxysmal AF, but a confirmatory ECG will not be necessary as AF is already documented in those patients.
- p. In patients with newly detected AF, the algorithm will still be used in follow up visits, in order to determine the rate of paroxysmal AF.
- q. At study entry the baseline characteristics will be collected, including:
 - i. Medical history and medication use (as part of the CGA).
 - ii. MoCA.
 - iii. Functional measures such as pattern of gait and muscle weakness (as part of the CGA) and basic measurements such as weight and blood pressure (as part of the CGA)
 - iv. Standard blood samples including kidney function, blood count, electrolytes and INR if applicable. Blood will be taken during the routine blood sampling, to assess the HS Troponine T, NTproBNP and GDF-15 at an external location (Dijklander Hospital). A separate protocol can be found on page 6 of this protocol.
- r. Information about the study will be available in print at every participating centre. This information folder is added as an attachment.
- s. Of all patients at least 3 measurements with the PPG based smartphone AF detection algorithm will be collected, including the measurement at study entry, during a 6 months follow-up period. After 3 years adverse events will be assessed.
- t. A designated research nurse will have access to the code list (patient identifier and study code) at each participating centre collect participating centres, collect data on the baseline characteristics, and the measurements with the PPG based smartphone AF detection algorithm.

[figure not shown]

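### The paroxysmal AF share (aim b) depends on negative app readings, but at follow-up only positive readings are reviewed or confirmed, so false negatives can relabel continuous AF as paroxysmal

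*Combined protocol and SAP*

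**What the plan says.** Aims of the project, item b, reads "To determine the rate of (paroxysmal) AF during follow-up visits", and Hypothesis, item b, gives the expected result: "We expect to find a rate of paroxysmal AF of 45 to 60" per cent. The method is in Methods, g. Procedure:

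- Item o, known AF: these patients are screened with the app, "making it possible to estimate the proportion of paroxysmal AF, but a confirmatory ECG will not be necessary as AF is already documented".
- Item p, newly detected AF: the app continues to be used at follow-up, for the same purpose.
- Item s: for each patient "at least 3 measurements with the PPG based smartphone AF detection algorithm will be collected, including the measurement at study entry". Methods item f leaves patients with fewer than three out of the analysis.
- Item n, review: "All positive measurements with the PPG based smartphone AF detection algorithm, will be assessed by an independent cardiologist".
- Item j: a 12-lead ECG follows when the app detects AF. Item o waives it in known AF.
- Item d: everyone has a 12-lead ECG at entry, whatever the app shows.
- Item i: readings spoiled by artefact are flagged and repeated.

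Neither the protocol nor the SAP gives a rule for calling AF paroxysmal. SAP section 1 lists no such variable, and sections 2 to 4 contain no analysis of aim b.

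**The concern.** Item o's reason for dropping the ECG is that AF is already on record. That reason covers a positive reading. What separates paroxysmal from continuous AF is a reading without AF, and at follow-up nothing checks one. A positive can be overturned on review; a negative cannot. Item i handles a visibly poor signal, but not a clean trace that the algorithm wrongly reads as non-AF.

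With three or more readings per patient, one miss can be enough to change the class, so a small miss rate per reading becomes a larger error rate per patient. Enrolling more patients would not reduce it. An observed share inside the hypothesised range could then partly reflect app misses, and the data as planned could not show how much.

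**Working it through.** The plan gives no precision or error calculation for aim b, so there is no figure of its own to reproduce.

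**Inputs from the documents.** Planned size: "We aim to include 1250 geriatric ambulatory patients". Prevalence: "We expect to find a rate of known AF of approximately 20%, and to find newly detected AF in 4 to 5" per cent. Hence known AF = 0.20 × 1250 = 250, and newly detected AF = 0.04 to 0.05 × 1250 = 50 to about 62. Readings per patient: three, the minimum. True paroxysmal share p: 0.45 and 0.60, the ends of the hypothesised range.

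**Assumptions.** Sensitivity per reading s = 0.90 to 0.98 (the protocol refers to another source for test characteristics); misses independent; no false positives left after review.

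**Step 1. Continuous AF with at least one miss.** With m unverified readings the share is 1 − s^m. The amount added to the apparent paroxysmal share is (1 − p)(1 − s^m).

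| s | m = 3 | added at p = 0.45 | added at p = 0.60 | m = 2 (entry ECG used) | added at p = 0.45 |
|---|---|---|---|---|---|
| 0.90 | 27.1% | 14.9 points | 10.8 | 19.0% | 10.5 points |
| 0.95 | 14.3% | 7.8 | 5.7 | 9.8% | 5.4 |
| 0.98 | 5.9% | 3.2 | 2.4 | 4.0% | 2.2 |

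Example: s = 0.95, m = 3 gives 1 − 0.857 = 0.143, and 0.55 × 0.143 = 0.078.

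**Step 2. Clustered misses.** If misses cluster within patients (beta-binomial, intra-patient correlation 0.3, assumed), the m = 3 column becomes 20.8%, 10.8% and 4.4%. At p = 0.45 that adds 11.4, 5.9 and 2.4 points.

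**Step 3. Dependence on the missing rule.** Step 1 counts any negative as paroxysmal. If at least one positive and one negative are required, the share of continuous AF mislabelled is 1 − s³ − (1 − s)³: 27.0%, 14.2% and 5.9%, almost the same. If two negatives were required it would be about 0.7% at s = 0.95, but no such rule is written.

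**Step 4. Scale.** The 95% half-width for 250 patients at p = 0.45 is 1.96 × √(0.45 × 0.55 / 250) = 0.062, about 6 points. With m = 3 and independent misses, the shift exceeds this at s = 0.95 but not at 0.98.

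**Step 5. The opposite error.** Let b be the chance that a patient with paroxysmal AF is in AF at a reading (assumed). If that patient is in AF at all three readings and all are detected, the AF looks continuous. Under the any-negative rule the apparent share is p(1 − (bs)³) + (1 − p)(1 − s³). Net bias at s = 0.95, in points:

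| b | p = 0.45 | p = 0.60 |
|---|---|---|
| 0.3 | +6.8 | +4.3 |
| 0.5 | +3.0 | −0.7 |
| 0.7 | −5.4 | −11.9 |

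Under the one-positive-and-one-negative rule at s = 0.95, the net bias was negative for every b tried from 0.1 to 0.9 (b = 0.5: −3.5 and −9.4).

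**The case against.** A reader might infer that aim b is biased upward overall. The documents do not support that. Step 5 shows either sign, depending on a classification rule that is not written and on how often paroxysmal patients are in AF when measured. Under the one-positive-and-one-negative rule, a miss can also erase a paroxysmal patient's only positive reading. What stands is narrower: false negatives in continuous AF push the share up, and the two errors cannot be relied on to cancel.

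A reader might also infer that the plan itself counts a patient read AF, AF, not AF as paroxysmal. No passage says so. That is a consequence of either natural rule, and the absence of any rule is part of the defect.

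The entry ECG is a real safeguard for the entry reading, and using it lowers the m = 3 figures to those for m = 2. It leaves the follow-up readings unchecked.

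Finally, the miss rate may be small. The protocol warns that "PPG measurements require good signal quality which may be affected by poorly perfused tissue or tremors", but the same paragraph says the algorithm was built to deal with this and has robust test characteristics. Artefacts are repeated and severe tremor is excluded. At a sensitivity of 99% the added amount with three unverified readings would be only 1.6 points at p = 0.45 and 1.2 at 0.60. That is a fair limit on the size, which the documents cannot settle. It does not answer the asymmetry in items j, n and o.

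**Conclusion.** The point holds in limited form. The label behind aim b requires a non-AF reading, follow-up negatives are never verified, and no rule for paroxysmal AF is stated. With three readings and sensitivity between 90% and 98%, 27% to 6% of patients in continuous AF could be relabelled (19% to 4% if the entry ECG settles the first reading). At a true 45%, that mechanism adds about 15 to 3 points (10 to 2 with the entry ECG), which ranges from well above to below sampling error. These figures rest on an assumed sensitivity, independent misses and one of the two natural rules; clustering makes them smaller. The net direction of bias in aim b is not established. Aim b is a stated aim but not the primary goal, so this is an inexpensive improvement and does not put the study's main result in doubt.

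**What to change.** 1. Extend item n so that the same independent cardiologists also read negative PPG traces in patients with known or newly detected AF. Add the definition to the SAP: a patient counts as paroxysmal only with at least one non-AF recording confirmed by that reading or by the entry 12-lead ECG. An unreadable trace does not count as non-AF.
2. In any case, for aim b use the entry ECG rhythm in place of the entry PPG result. Report beside the observed proportion a sensitivity analysis over a stated range of Se, using 1 − Se^m, where m counts only the unverified readings (m = 2 with three readings and an entry ECG). State that under-sampling acts in the opposite direction.

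Cost: one sentence in items n and o and a short SAP entry. At three readings each, item 1 concerns about 250 × 3 = 750 traces in known AF, plus 150 to about 188 from the 50 to 62 newly detected patients. The total is higher if patients have more readings; the added work is lower because only negatives are new. Negative traces must be kept. Item 2 is analysis only. The reported paroxysmal rate may come out somewhat lower.

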 - c. The patient has a severe tremor, from whatever cause, and thus is unable to use the PPG based smartphone AF detection algorithm.
- f. Exclusion from analysis:
 - a. Less than three measurements with the PPG based smartphone AF detection are performed.
- g. Procedure (See also Figure 1, on page 5):
 - a. All participating patients will be allocated a study number. The allocation of study numbers will be coordinated by the research nurse, in collaboration with the local investigator and secretary. To ensure patient privacy, it is not allowed to use the hospital's patient number as the study number. Predefined study numbers will be provided to each centre.
 - b. The study number will be communicated with the physician by the secretary, and added to the electronic hospital files.
 - c. A CGA will be performed at baseline.
 - d. A 12 lead ECG will be performed at study entry to assess the baseline heart rhythm.
 - e. At every visit to the outpatient service one measurement with the PPG based smartphone AF detection algorithm will be performed.
 - f. The application will be made available for patients to install on their own smartphone, or their caretaker's.
 - g. Before each measurement the physician/patient/caretaker enters the patient's study number into the PPG app, which allows the investigators to register which measurement belongs to which participant, without accessing their medical files.
 - h. Coded, raw data will be analysed by the app, and results automatically sent by email to the principle investigator ([name]).
 - i. The smartphone shows the measurement in real time. In case of artefacts due to movement or otherwise, the PPG based smartphone AF detection algorithm will reveal this and a repeat measurement will be performed.
 - j. In case the PPG based smartphone AF detection algorithm detects AF, a 12 lead ECG is performed to confirm and document the diagnosis of AF and appropriate treatment will be initiated by the treating physician.

- k. If AF is detected at home, patients will be invited for the 12 lead ECG in the outpatient clinic.
 - l. Only patients who are known with AF and have an ECG or Holter registration showing AF in their medical record will be classified as patients with 'known AF'.

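### After study entry, negative PPG readings in AF patients are not checked and paroxysmal AF has no classification rule, so the aim b proportion cannot be read at face value

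*Combined protocol and SAP*

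**What the plan says.** Aim b is "To determine the rate of (paroxysmal) AF during follow-up visits". Hypothesis b reads "We expect to find a rate of paroxysmal AF of 45 to 60" per cent, without a denominator; I read it as a share of AF patients.

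The Methods (g. Procedure) supply the data as follows:

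- Item d: "A 12 lead ECG will be performed at study entry to assess the baseline heart rhythm". No exception is made for known AF.
- Item s: "Of all patients at least 3 measurements with the PPG based smartphone AF detection algorithm will be collected, including the measurement at study entry". Three is a minimum, and items f and k allow readings at home.
- Item i: a reading that the app flags for artefact is repeated.
- Item j: a 12-lead ECG follows when the PPG algorithm detects AF.
- Item n: "All positive measurements with the PPG based smartphone AF detection algorithm, will be assessed by an independent cardiologist".
- Item o: known-AF patients are screened in the same way to estimate the paroxysmal proportion, but "a confirmatory ECG will not be necessary as AF is already documented in those patients".
- Item p: in newly detected AF the algorithm continues at follow-up visits for the same purpose.

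No item says which pattern of readings makes a patient paroxysmal. The background text calls the test characteristics robust and refers to a publication; it gives no sensitivity. The SAP (sections 1 to 4) contains no analysis of aim b and no comparison of PPG with ECG.

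**The concern.** In a patient whose AF is already documented, another positive reading adds little. The informative result is a reading without AF, because any paroxysmal rule built on these readings needs at least one. Verification is placed on the other side: items j and n act on positive readings only. The waiver in item o does not show this gap by itself, since it concerns the ECG that would follow a positive reading. The gap appears when items j, n, o and p are read together.

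A patient who is always in AF and has one missed reading can therefore be counted as paroxysmal. The artefact repeat in item i does not catch a false negative with a clean-looking signal. At stake is whether an observed 45 to 60% says anything about hypothesis b. The entry visit provides a PPG reading and a 12-lead ECG on the same patients, which would show how often the PPG misses AF, but the SAP does not pair them.

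**Working it through.** The plan states no calculation for aim b, so there is none to reproduce.

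**Inputs from the documents.** N = 1250 (Design, item b); known AF about 20% (Hypothesis a), so 1250 × 0.20 = 250 patients; at least k = 3 readings (item s); expected paroxysmal share 45 to 60% (Hypothesis b).

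**Assumptions.** PPG sensitivity s = 0.90, 0.95 or 0.98; specificity 1; true paroxysmal share 45%.

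**1. One negative reading suffices, errors are independent, all true paroxysmal cases are recognised.** Share of always-in-AF patients mislabelled = 1 − s³. Apparent share = 0.45 + 0.55 × (1 − s³).

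| s | 1 − s³ | Apparent share |
|---|---|---|
| 0.90 | 0.271 | 0.599 |
| 0.95 | 0.143 | 0.528 |
| 0.98 | 0.059 | 0.482 |

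At s = 0.99 the apparent share is 0.466, a shift of less than 2 points. With six readings, 1 − s⁶ = 0.469, 0.265 and 0.114 at s = 0.90, 0.95 and 0.98. For scale, the 95% half-width at n = 250 is 1.96 × √(0.45 × 0.55 / 250) = 0.062, so the shift of about 8 points at s = 0.95 exceeds sampling error.

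**2. The entry reading is replaced by the entry ECG.** Two PPG readings remain, and the mislabelled share is 1 − s² = 0.190, 0.098 and 0.040. The apparent share becomes 0.45 + 0.55 × (1 − s²) = 0.5545, 0.504 and 0.472. The ECG removes part of the error but not all of it.

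**3. Errors fully clustered within patients.** The same patients are missed every time, so mislabelling is 1 − s and does not grow with more readings. The apparent share at s = 0.90 is 0.45 + 0.55 × 0.10 = 0.505.

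**4. Sparse sampling of true paroxysmal AF.** Let a paroxysmal patient be in AF a fraction b of the time, with three independent readings.

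- *Rule: at least one positive and one negative.* Recognised share of paroxysmal patients = 1 − (bs)³ − (1 − bs)³. Mislabelled always-in-AF patients = 1 − s³ − (1 − s)³, which is 0.270 at s = 0.90. With b = 0.3 and s = 0.90, bs = 0.27 and the recognised share is 1 − 0.020 − 0.389 = 0.591. The apparent share is 0.45 × 0.591 + 0.55 × 0.270 = 0.415. At s = 0.95 and 0.98 it is 0.353 and 0.313. All are below 45%.
- *Rule: any negative.* Recognised share = 1 − (bs)³. With b = 0.7 and s = 0.95, bs = 0.665 and the recognised share is 0.706. The apparent share is 0.45 × 0.706 + 0.55 × 0.143 = 0.396, also below 45%. With b = 0.3 and s = 0.95 it is 0.518, above 45%.

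**5. What the entry visit could yield.** If paroxysmal patients are in AF at entry 30% of the time (assumed), known AF alone gives 250 × (0.55 + 0.45 × 0.30) = 171 ECG-AF pairs at a 45% paroxysmal share, and 250 × (0.40 + 0.60 × 0.30) = 145 at 60%. With 150 pairs and s = 0.95, the Wilson 95% interval is about 0.90 to 0.97.

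**The case against.** The strongest reply is that the one-negative rule is not in the plan. That is correct, and the missing rule is part of the point. Without it nobody can say what the reported proportion will mean. The false-negative problem also survives a stricter rule: with independent errors, requiring one positive and one negative reading mislabels 27.0% instead of 27.1% at sensitivity 0.90.

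Second, a reader might infer that aim b is inflated, because false negatives turn continuous AF into apparent paroxysmal AF. The documents do not support that as a net statement. Few readings can also miss true paroxysmal AF, and step 4 shows results below the true value under either rule. Only the false-negative component points upward.

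Third, independence is an assumption. Poor perfusion, which the background names as a cause of poor signal, may well be a lasting feature of the patient. Full clustering cuts the apparent share at 0.90 from about 60% to 50.5%, and under the stricter rule the mislabelling disappears.

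Fourth, a reader might infer that negative readings are never verified. The entry ECG gives the entry reading a reference rhythm, although the plan does not say that it will be used this way. Severe tremor is an exclusion criterion and flagged artefacts are repeated, so some causes of error are already reduced.

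Fifth, one might infer that missed readings bias the yield of newly detected AF. Aim a is the rate found with PPG screening, so misses belong to that yield. What stands is narrower: item m requires PPG detection first, so a patient without known AF who is in AF on the entry ECG but PPG-negative is not counted, and no table would show it.

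**Conclusion.** The point holds in limited form. Follow-up negative readings in AF patients have no ECG or reviewer check, the paroxysmal rule is unstated, and the SAP leaves the entry PPG and ECG unpaired. A raw 45 to 60% therefore cannot be taken at face value.

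The false-negative component could be large: 15 points at sensitivity 0.90 and 8 at 0.95, given independent errors, a one-negative rule and full recognition of true cases. It could also be small: 3 points at 0.98 and less than 2 at 0.99. A shift across the whole hypothesised range is the extreme case, needing all three conditions and a sensitivity of 0.90, a value the documents do not give. The net direction is unknown. Aim b is a descriptive aim with no planned test, so this is a worthwhile, cheap improvement and not a threat to the main aim.

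**What to change.** Add to the SAP:

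1. A cross-tabulation of the entry PPG against the entry 12-lead ECG in all patients, with sensitivity and specificity and 95% confidence intervals.
2. Use of the ECG, not the PPG, as the entry rhythm when AF patients are classified.
3. The rule that classifies paroxysmal AF from the readings, with its denominator.
4. The raw paroxysmal proportion together with a sensitivity analysis over the estimated PPG sensitivity, under both independent and within-patient-clustered errors. Interpret 45 to 60% in that light, and state that sparse sampling may still hide true paroxysmal AF. A single corrected figure would claim too much, because it would have to assume one error pattern.
5. The number of patients without known AF who were in AF on the entry ECG but PPG-negative.

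The data are already to be collected; no visit or ECG is added. The cost is a little more analysis, a wider range for the paroxysmal proportion, and reliance on the routine reading of the entry ECG, because the plan provides an independent research read only for ECGs that confirm newly detected AF.
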